4.1 Safety

All adverse events will have severity graded according to the National Cancer Institute (NCI) Common Terminology Criteria for Adverse Events (CTCAE) Version 4.0

This will be based on combining all the AEs, SAEs and SUSARs, and any other source of adverse events (e.g. unscheduled bloods case report form).

For each type of event, for each patient, the maximum grade will be obtained.

4.1.1 Number of patients with each type of event (each patient only counted once on each row)

Event Term	Grade 1	Grade 2	Grade 3	Grade 4
Abdominal pain				
Anorexia				
Ascites				
Back pain				
Bronchospasm				
Cardiac disorders				
Constipation				
Cough				
Diarrhea				
Dry mouth				
Dyspepsia				
Dyspnea				
Electrocardiogram QT corrected interval prolonged				
Fatigue				
Flu like symptoms				
Gastritis				
etc				

- Several versions of the above table:

AEs post-TACE:

- AEs on the day after BTG-002814 treatment only
- AEs after BTG treatment and up to (but not including) the day of surgery
- AEs after BTG treatment and up to (but not including) the day of surgery, which are considered to be related to vandetanib
- AEs after BTG treatment and up to (but not including) the day of surgery, which are considered to be related to TACE

AEs post Surgery:

- AEs only occurring after surgery (up to the end of the 32-day follow up)
- All AEs occurring at any time from the delivery of BTG treatment

4.1.2 Number of events with each type of event (a patient can be counted more than once on each row if they experienced the same event several times)

Event Term	Grade 1	Grade 2	Grade 3	Grade 4
Abdominal pain				
Anorexia				
Ascites				
Back pain				
Bronchospasm				
Cardiac disorders				
Constipation				
Cough				
Diarrhea				
Dry mouth				
Dyspepsia				
Dyspnea				
Electrocardiogram QT corrected interval prolonged				
Fatigue				
Flu like symptoms				
Gastritis				
etc				

- Several versions of the above table:

AEs post-TACE:

- AEs on the day after BTG treatment only
- AEs after BTG-002814 treatment and up to (but not including) the day of surgery
- AEs after BTG-002814 treatment and up to (but not including) the day of surgery, which are considered to be related to vandetanib
- AEs after BTG-002814 treatment and up to (but not including) the day of surgery, which are considered to be related to TACE

AEs post Surgery:

- AEs only occurring after surgery (up to the end of the 32-day follow up)
- All AEs occurring at any time from the delivery of BTG treatment
- For any grade 3 or 4 event, look at time to the first occurrence of the grade 3/4 event (BTG treatment day is Day 0): do scatter plot of these

4.1.3 Examine which grade 3 or 4 AEs that occur any time after BTG-002814 delivery were already present at baseline in the patient (i.e. pre-treatment).

Descriptively, provide summary of which had got worse.

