## 4.5. Study Endpoints

### 4.5.1. Co-Primary Endpoints

- Adverse events (AEs) related to treatment with BTG-002814 using the standardised grading criteria (National Cancer Institute Common Terminology Criteria for Adverse Events Version 4.0 (NCI-CTCAE v4.0))
- Concentration of vandetanib and N-desmethyl vandetanib in plasma and in resected liver tissue following treatment with BTG-002814.

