## 9.2. Statistical Analysis

The statistical analysis plan will be a separate document and will be updated as required prior to the analysis, in association with any protocol amendments. The plan will include descriptions of tables, listings and figures and will describe statistical programming considerations.

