## **9.5. Safety Analyses**

All safety results will be presented overall and by disease (HCC or mCRC):

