### **9.5.1. Adverse Events**

Adverse events will be graded by the Investigators using the NCI CTCAE v4.0 scale, and coded using MedDRA (the current version at the time of coding).

The number (n) and percentages (%) of patients affected by at least one AE, as well as the number of patients affected by at least one AE with causal relationship to the study treatment, will be summarised firstly overall, then by system/organ class and preferred term (MedDRA). Adverse events will also be tabulated by intensity, treatment for the AE, outcome and causality.

Deaths, SAEs, treatment-related complications, AEs leading to withdrawal and Unexpected Adverse Events (UAE) will be listed separately.

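### SAP 4.1 does not fully cover the co-primary safety endpoint: its related-AE tables stop before the day of surgery, with no any-related count and no split by disease

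*SAP*

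**What the plan says.** **Endpoint.** Protocol 4.5.1 gives the first co-primary endpoint as "Adverse events (AEs) related to treatment with BTG-002814 using the standardised grading criteria", meaning CTCAE version 4.0. SAP section 1 repeats it. Neither sets a time limit at surgery.

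**Protocol analysis.** Section 9.5.1 asks for the number and percentage of patients with any AE, and for the "number of patients affected by at least one AE with causal relationship to the study treatment", first overall and then by system organ class and preferred term. It also asks for tabulation by causality and for separate listings that include deaths, SAEs and treatment-related complications. Section 9.5 adds: "All safety results will be presented overall and by disease". Section 9.2.1 likewise asks for separate HCC and mCRC results. Section 9.2 leaves the layout of outputs to the SAP: "The plan will include descriptions of tables, listings and figures".

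**SAP tables.** Section 4.1.1 counts patients and 4.1.2 counts events. Each lists the same six versions of one shell, with event terms as rows and grades 1 to 4 as columns. The two versions that select on relatedness are "AEs after BTG treatment and up to (but not including) the day of surgery, which are considered to be related to vandetanib" and "AEs after BTG treatment and up to (but not including) the day of surgery, which are considered to be related to TACE". Section 4.1.2 repeats them, for example "AEs after BTG-002814 treatment and up to (but not including) the day of surgery, which are considered to be related to vandetanib". The post-surgery version is "AEs only occurring after surgery (up to the end of the 32-day follow up", with no causality condition.

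**Data collected.** Protocol 7.3.21 and 8.1.3 record AEs from consent to the last visit, and relationship to treatment is recorded for each AE. Section 8.1.4 has vandetanib judged separately from the beads and TACE procedure. Under 6.1.4, surgery is 7 to 21 days after treatment and follow-up runs 28 to 32 days beyond it.

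**The concern.** Safety is a co-primary endpoint of a first-in-human study, and the endpoint is limited to related AEs. If the SAP is programmed as written, the final tables would show related AEs only for the stretch between treatment and the eve of surgery. A vandetanib-related event that starts after resection would be counted, but nothing in the table would mark it as related.

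The protocol does treat late relatedness as relevant. Related AEs still present at Visit 6 are recorded as ongoing (7.2.7 and 8.1.3), and SAEs judged related are reportable even after that visit (8.1.5). These are collection rules and give no event rate, but they show that the endpoint was not meant to close at surgery.

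The SAP is also where the table descriptions are meant to be. A reader of SAP 4.1 alone would find neither the any-related count nor the split by disease.

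**Working it through.** No sample-size or power figure bears on this point: protocol 9.1 says the study is not powered. The check compares the SAP table list with the protocol, then counts days and bounds.

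**1. The six versions in SAP 4.1** (the same list in 4.1.1 and 4.1.2)

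| Version | Period | Selects related AEs? | Split by disease? |
|---|---|---|---|
| 1 | Day after treatment | No | No |
| 2 | Treatment to day before surgery | No | No |
| 3 | Treatment to day before surgery | Yes, vandetanib | No |
| 4 | Treatment to day before surgery | Yes, TACE | No |
| 5 | After surgery | No | No |
| 6 | Any time from treatment | No | No |

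Two of six select on relatedness, and both end before the day of surgery. None of six shows related AEs from the day of surgery to Visit 6, combines the two attributions, or is split by disease. Elsewhere the SAP does indicate disease: in 4.2 for concentrations, in 5 for most imaging and biomarker results, and in 8 for deaths and withdrawals.

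Only version 6 clearly includes the day of surgery, although AEs are recorded on that day (protocol 7.2.6, Visit 5).

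**2. Share of the follow-up period covered**

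Inputs, from protocol 6.1.4: surgery on Day S, with S = 7 to 21 and treatment on Day 0; last visit on Day S + F, with F = 28 to 32.

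- Days from treatment to last visit, inclusive: S + F + 1.
- Days in the related-AE tables (Day 0 to Day S − 1): S.
- Lowest coverage, S = 7 and F = 32: 7 / (7 + 32 + 1) = 7/40 = 17.5%.
- Highest coverage, S = 21 and F = 28: 21 / (21 + 28 + 1) = 21/50 = 42.0%.
- Days without a related-AE table: F + 1 = 29 to 33 per patient, or 58.0% to 82.5% of the period.

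**3. Can the any-related count be rebuilt?**

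A patient may be in both the vandetanib and the TACE version, and on several term rows. The number of patients with any related AE is then fixed only within bounds: at least the largest single count, at most the smaller of n and the sum of the counts. With assumed counts, for illustration only, and n = 12:

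- 3 patients with a vandetanib-related AE and 4 with a TACE-related AE: at least max(3, 4) = 4, at most min(12, 3 + 4) = 7.
- Term rows of 3, 2, 2 and 1 patients within one version: at least 3, at most min(12, 8) = 8.

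So the figure that protocol 9.5.1 asks for cannot be recovered from the planned tables, even for the period before surgery.

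**4. Do other SAP sections fill the gap?**

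Section 3 counts TACE-related problems at delivery, which does not cover vandetanib. Section 8 gives cause of death without relatedness. Section 9 covers laboratory values, ECG, vital signs and physical examination; its only listing is of laboratory data.

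**The case against.** **Surgery confounds attribution.** After a liver resection, judging whether an AE comes from the beads, the drug or the operation is hard, so a related-AE table that stops before surgery is a reasonable analysis. This stands as a reason to keep that view. It does not justify having no other, because the investigator's causality judgement is still collected after surgery.

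**The protocol still governs.** The SAP says it follows protocol version 6 and nowhere cancels 9.5 or 9.5.1. The any-related count, the split by disease and the listings of deaths, SAEs and treatment-related complications therefore remain pre-specified, with no surgical cut-off. This stands: the SAP fails to carry text over and does not contradict it. But protocol 9.2 gives the table descriptions to the SAP, and the SAP describes no AE listing by causality.

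**Nothing is lost and no decision depends on it.** Post-surgery AEs are in versions 5 and 6. The safety committee reviews all AEs and SAEs, the interim review uses all AEs, and the study is descriptive. This also stands. The gap is in the labelling of final results.

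**Stronger readings that a reader might infer.** One is that SAP 4.1 misses the co-primary endpoint altogether. It does not: related AEs before surgery are tabulated by term and grade, by patients and by events. Another is that 58.0% to 82.5% of related AEs would go unreported. Those figures count days, and the documents give no event rate. Nor does the advice on sun exposure for at least four weeks (protocol 6.1.2) show that late related events are expected; it is precautionary.

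**Conclusion.** The concern holds in part, and the SAP should be corrected. SAP 4.1 does not fully cover the co-primary safety endpoint: two of six table versions select related AEs, and both end before the day of surgery, leaving 29 to 33 days per patient without a related-AE table. That cut-off bears on the endpoint itself. The missing any-related count and split by disease depart from the protocol's analysis text (9.2.1, 9.5 and 9.5.1) and not from the endpoint wording in 4.5.1.

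The day count assumes the planned windows for surgery and last visit. The number of related AEs affected cannot be computed from the documents.

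One definition is open. The protocol collects separate judgements for vandetanib and for the beads and TACE procedure, but does not say how they combine into relatedness to BTG-002814. Counting an AE related to either component is a natural rule, but it is an assumption until the SAP states it.

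**What to change.** In the SAP:

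- Keep the two pre-surgery related versions.
- Add one related-AE table for the whole period from treatment to Visit 6 to each of 4.1.1 and 4.1.2. Show relatedness to vandetanib and to beads/TACE, in columns overall, HCC and mCRC. In 4.1.1, add a top row for any AE related to BTG-002814 as n (%), each patient counted once.
- State how the two causality judgements map to relatedness to BTG-002814, for example related to either.
- Show the other 4.1 tables overall and by disease.
- Minor: state which version holds AEs with onset on the day of surgery. Only the onset date is recorded, so events before and after the operation on that day may not be separable.
- Minor: the shells stop at grade 4, so show any fatal AE with its causality, consistent with the separate listing of deaths in protocol 9.5.1.

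**Cost.** Six versions in two sections make 12 tables; one more per section makes (6 + 1) × 2 = 14, with disease columns added. Many cells will be sparse with 12 to 14 patients. Everything comes from AE term, grade, onset date and causality, which are already recorded. The change needs SAP wording and programming, with no new data and no protocol amendment.

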4.2 Drug concentrations

These analyses will be performed by BTG.

4.2.1 Plasma

For each patient, obtain the plasma time-concentration curve for:

- vandetanib
- N-desmethyl metabolite

Each plot would be indicated as to whether the patient had HCC or mCRC.

Time points are:

- Day of BTG treatment but before administration (0 hours)
- 2 hours post-BTG treatment
- 4 hours post-BTG treatment
- 24 hours post-BTG treatment
- 3 days to 1 day prior to surgery
- 28-32 days post-surgery.

PK parameters such as T_{max} (time taken to reach the highest concentration) and C_{max} (the maximum concentration) could be obtained, and use summary statistics to describe these. Other standard PK parameters can be included (e.g. AUC to 32 days, and AUC to the end of the observation time period), as determined by the investigators, such as $T_{1/2}$, clearance CL/F , and volume of distribution (V_z/F).

4.2.2 Resected tissue

For each patient, provide a concentration-time plot for:

- vandetanib
- N-desmethyl metabolite

(concentration as the y-axis and time as the x-axis).

Each plot would be indicated as to whether the patient had HCC or mCRC.

This will be for:

- malignant tissue – three measurements for each patient:
 - Centre of tumour
 - Mid tumour
 - Edge of tumour
- non-malignant tissue
 - 1 cm from the edge of the tumour
- paired samples (difference, per patient, using malignant (based on the average of the 3 locations/samples) minus non-malignant values). Can be analysed using a t-test or non-parametric test
- Describe technical reasons for missing data points

5. Secondary objectives/outcomes (other blood, tissue and imaging markers)

5.1 Distribution of BTG-002814

The distribution of BTG-002814 within the tumour vasculature and regions of interest will be assessed on non-contrast enhanced imaging. The findings will be summarised descriptively, and HCC or mCRC will be indicated.

5.2 Histopathology of resected liver

An evaluation of histopathological features in both malignant and non-malignant liver tissue from the surgical specimen will be performed. The extent of tumour necrosis, viable tumour and any vascular changes observed will be summarised descriptively.

5.3 3D modelling

Associations between the distribution of BTG-002814 on imaging and within the pathological specimen will be described using 3D modelling, and HCC or mCRC will be indicated.

5.4 Blood flow following embolisation

Assessment of changes in blood flow will be assessed using DCE-MRI following treatment with BTG-002814. For individual patients, the following parameters will be derived from DCE-MRI scans at visits 1 and 2 (pre-treatment) and visit 4 (post-treatment), and HCC or mCRC will be indicated.

Dual-input single-compartment model

- Arterial flow (ml/min/100g)
- Portal venous flow (ml/min/100g)
- Arterial fraction (%)
- Mean transit time (seconds)
- Distribution volume (%)

Tofts model

- Volume transfer constant between plasma and extravascular extracellular space - K^{trans} (min^{-1})
- Volume transfer constant between extravascular extracellular space and plasma - K_{ep} (min^{-1})
- Volume of extravascular extracellular space per unit volume of tissue - V_e (%)

Semi-quantitative analysis

- Time-to-peak – TTP (seconds)
- Area under curve at 60 seconds (mmol/L.s)
- Peak Gadolinium concentrations – C_{peak} (mmol/L)
- Upslope - C_{peak}/TTP (mmol/L.s)

For each patient, perfusion parameters for visit 1 and 2 will be used to estimate intra-patient reproducibility. Visit 4 parameters from each patient will be used to measure potential changes following treatment with BTG-002814, in the context of the baseline reproducibility for each patient, and HCC or mCRC will be indicated.

The same principles will be applied to perfusion CT parameters shown below.

Maximum slope method:

- Arterial flow (mL/min/100ml)
- Portal flow (mL/min/100ml)
- Perfusion index

Patlak model:

- Blood volume (ml/ml tissue)
- Arterial perfusion (mL/min/100ml)
- Flow extraction product (ml/min/100ml)

For changes observed within each patient, data from DCE-MRI will be compared to changes observed in perfusion CT at the same timepoints to confirm the veracity of potential changes observed in blood flow.

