#### 7.2.2. Visit 1: Baseline Visit (up to 7 days before treatment)

Following fulfilment of the inclusion and exclusion criteria and registration of the patient, the following assessments and procedures are required to be done within 7 days prior to treatment with BTG-002814:

- Liver MRI, incorporating Dynamic Contrast Enhanced MRI (DCE-MRI), as described in section 7.3.11
- CT scan of chest, abdomen & pelvis, incorporating perfusion CT of liver, as described in section 7.3.11
- Blood sample for biomarkers, as described in section 7.3.13
- Blood sample for serum tumour markers, as described in section 7.3.10
- Record any concomitant medications, as described in section 7.3.20
- Adverse events will be recorded and assessed as described in section 7.3.21

The following tests and procedures do not need to be repeated if carried out within 7 days prior to treatment with BTG-002814 as part of screening work up:

- 
- 

Physical examination will be conducted, as described in section 7.3.4

Vital signs will be taken, as described in section 7.3.5

- Performance status will be assessed, as described in section 7.3.6
- Blood samples for biochemistry, haematology and coagulation, as described in section 7.3.8
- A 12-lead ECG will be done as described in section 7.3.12
- Blood sample for serum pregnancy test for all patients of child-bearing potential, as described in section 7.3.9

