#### Pre-treatment Assessments

The following scans will be performed within a day prior to administration of BTG-002814:

- Liver MRI, incorporating DCE-MRI, as described in section 7.3.11
- CT scan of chest, abdomen & pelvis, incorporating perfusion CT of liver, as described in section 7.3.11

The following assessments and procedures will be performed on the day of treatment prior to administration of BTG-002814:

- Vital signs will be taken, as described in section 7.3.5
- Record any concomitant medications, as described in section 7.3.20
- Record any adverse events, as described in section 7.3.21
- A 12-lead ECG will be taken, as described in section 7.3.12
- Blood sample for biomarkers, as described in section 7.3.13
- Blood sample for serum tumour markers, as described in section 7.3.10
- Blood sample for vandetanib and metabolite analysis, as described in section 7.3.14

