## DCE-MRI

For DCE-MRI, patients will lie supine on the scanner table and an intravenous cannula placed in the antecubital fossa. No oral contrast is required. After acquisition of standard clinical MRI liver sequences, T1 mapping will be performed using three-dimensional volumetric gradient echo imaging with varying flip angles. A series of T1-weighted three-dimensional volumetric images will be acquired at baseline and at short intervals during administration of a bolus of intravenous paramagnetic MR contrast agent at a rate of 3-5 mL/s. Each acquisition takes approximately 5 seconds during which time patients are asked to hold their breath in full expiration or if necessary to breathe in a shallow fashion. The entire post contrast DCE series takes approximately 3-5 minutes.

Liver parenchyma and tumour signal intensity curves will be used to calculate semiquantitative and quantitative tissue parameters describing tumour perfusion, blood flow and vascularity, using a compartment model with an arterial and portal venous input function.

Assessment of changes in blood flow on DCE-MRI following treatment with BTG-002814.  $K^{trans}$ ,  $K^{ep}$  and  $V^e$  will be derived from DCE-MRI images.

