
 • Distribution of BTG-002814 on non-contrast enhanced imaging of tumour vasculature and regions of interest using 4D CT • Evaluation of histopathological features in the surgical specimen (malignant and non-malignant liver tissue): tumour necrosis, viable tumour, vascular changes • Changes in blood flow on DCE-MRI following treatment with BTG-002814. The following parameters will be derived from DCE-MRI images: K_{trans}, K_{ep} and V_e
Exploratory Objectives and Outcomes

 • Study blood biomarkers with the potential to identify patients likely to respond to treatment with BTG-002814 • Study tissue biomarkers to explore key immune, inflammatory and drug related mechanisms • Correlate the distribution of BTG-002814 on imaging with pathology by 3D modelling

Study Schema

2. Baseline characteristics

Table showing the number of patients (categorical variables) or the mean/median and range (for continuous variables), for:

- Gender, age, ethnicity, ECOG performance status.
- HCC or colorectal cancer
- For HCC, state whether histological or radiological diagnosis
- Location (liver segments) and characteristics of the tumour: number of liver lesions, sum of longest diameters (mm).
- Vital signs: blood pressure, weight, height, heart rate, ECG results (including QTc interval)
- Key baseline laboratory measures: Hemoglobin, absolute neutrophil count, platelets, serum bilirubin, serum creatinine, liver function tests, and others agreed by the investigators (from the screening case report form Visit 0).
- Child-Pugh score and serum alpha-fetoprotein level (HCC patients only)
- Tumour markers (colorectal cancer patients only): CEA, CA19-9, CA125
- Previous systemic treatments for cancer

Provide in the text or CONSORT diagram:

- The number of patients who were ineligible, and the reasons why they were ineligible
- The number of patients who were recruited to the trial but withdrew later on, and the reasons (if available)
- List any possible major protocol violations or ineligibility criteria that would lead to the patient not being included in the analysis. This information is not in the main database but would be summarised in a table.

3. BTG-002814 treatment

Assessments on treatment day

Measurements	Mean/median, and range, and standard deviation
Before BTG-002814 treatment (absolute values)	
Blood pressure	
Heart rate	
ECG QTc interval (state method used for calculation)	

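### SAP 5.4 judges each patient's Visit 4 blood-flow change against reproducibility from that patient's single Visit 1–2 pair; adding a pooled within-patient SD beside the pairs would usually give a steadier yardstick

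*SAP*

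**What the plan says.** SAP 5.4 derives perfusion parameters for individual patients at Visits 1 and 2 (pre-treatment) and Visit 4 (post-treatment). On reproducibility it says: "For each patient, perfusion parameters for visit 1 and 2 will be used to estimate intra-patient reproducibility". Visit 4 is then used to look for change after treatment "in the context of the baseline reproducibility for each patient". For the other modality: "The same principles will be applied to perfusion CT parameters shown below".

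The protocol fixes how many baseline scans there are.
- Visit 1 (Protocol 7.2.2) has one DCE-MRI and one perfusion CT, under the rule that "the following assessments and procedures are required to be done within 7 days prior to treatment with BTG-002814".
- Visit 2 (Protocol 7.2.3, Pre-treatment Assessments) has one more of each: "The following scans will be performed within a day prior to administration of BTG-002814".

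Neither document mentions a within-patient SD pooled over patients, a repeatability coefficient, or a rule for calling a change real. Protocol 9.4.5 asks only for a descriptive summary of the DCE-MRI parameters, and Protocol 9.1 says the study is not powered.

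**The concern.** The second baseline scan makes it possible to estimate scan-to-scan noise. Used one patient at a time, it yields a noise estimate from a single difference. Two baseline scans that happen to agree make the yardstick far too short, and an ordinary Visit 4 value then looks like a treatment effect. Two that happen to disagree can hide a real change. The impression of whose blood flow moved beyond noise would depend partly on luck at baseline.

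At stake is the per-patient reading of one secondary endpoint, change in blood flow on DCE-MRI, and its perfusion-CT counterpart.

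**Working it through.** The documents give no repeatability figure, so there is none to reproduce. The check asks how well one pair, and then all pairs together, estimate a within-patient SD.

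**Inputs.** Two pre-treatment scans per patient and modality (Protocol 7.2.2, 7.2.3). Target of 12 patients, 6 with HCC and 6 with mCRC (Protocol 9.1). SAP 5.4 lists 5 + 3 + 4 = 12 DCE-MRI parameters and 3 + 3 = 6 perfusion-CT parameters, 18 in all.

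**Assumptions.** Independent normal errors with equal variance across visits, no systematic shift from Visit 1 to Visit 2, one value per parameter, region and scan, and no missing scans.

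**Estimators.** With d = V1 − V2:
- own pair: s = |d| / √2, with 1 df;
- pooled over n patients: s = √(Σd² / 2n), with n df.

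**Interval for the true SD.** As multiples of the estimate, the 95% limits are √(df / χ²) at the upper and lower 2.5% points.

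| Basis | df | χ² points (2.5%, 97.5%) | 95% CI, multiples of the estimate |
|---|---|---|---|
| Own pair | 1 | 0.00098, 5.02 | 0.45 to 31.9 |
| Pooled over 6 | 6 | 1.24, 14.45 | 0.64 to 2.20 |
| Pooled over 12 | 12 | 4.40, 23.34 | 0.72 to 1.65 |

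**Spread between patients from chance alone.** If all 12 patients had the same true SD, the ratio of the largest to the smallest own-pair SD would have a median of 27 (simulation, 400,000 draws). The chance that an own-pair SD is below half the true value is P(χ² on 1 df < 0.25) = 38%.

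None of these figures needs a decision rule.

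**If patients truly differ.** Let true SDs vary between patients (lognormal, an assumption; 400,000 draws). The chance that the estimate is within a factor of 2 of that patient's own true SD is:

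| CV of true SDs | Own pair | Pooled over 12 | Pooled over 6 |
|---|---|---|---|
| 0 | 57% | 99.6% | 96% |
| 0.3 | 57% | 94% | 89% |
| 0.5 | 57% | 80% | 78% |
| 0.8 | 57% | 61% | 63% |

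On this measure, pooling over 12 stops being better at a CV of about 0.9.

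**Extreme patients.** Same measure, pooled over 12, at CV 0.3, 0.5 and 0.8: noisiest patient 82%, 59% and 39%; least variable patient 75%, 31% and 7%. The own pair stays at 57%.

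**Reference limit.** With change = V4 − (V1 + V2)/2, the variance under no effect is σ² + σ²/2 = 1.5σ². A 95% limit is therefore t(df) × √1.5 × pooled SD: 2.179 × 1.225 = 2.67 pooled SDs at 12 df, and 2.447 × 1.225 = 3.00 at 6 df.

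**Chance marks.** 18 parameters × 12 patients = 216 values per region. At 5%, 216 × 0.05 = 10.8, so about 11 unchanged values would fall outside the limit.

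**The case against.** Five points can be made for the plan.

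- **No statistic or threshold is named.** The wording could be met by plotting three values per patient and judging them by eye. So although a reader might infer that the plan has a known, high false-positive rate, the documents do not support that: there is no rule whose error rate could be computed. The own-pair reading still follows, because the text ties reproducibility to each patient twice, and the interval and ratio figures hold without a rule.
- **Nothing depends on it.** The study is descriptive and no decision uses the per-patient reading. This stands, and it limits the weight of the point.
- **Pooling rests on an unseen quantity.** This stands in part. The documents give no repeatability data, and pooling does worse than the own pair for the noisiest patient at CV 0.8 and for the least variable patient at CV 0.5 and 0.8. A reader might infer that pooling should replace the individual pairs; these figures argue against that.
- **Several regions could add information.** Protocol 7.3.11 says: "Liver parenchyma and tumour signal intensity curves will be used to calculate semiquantitative and quantitative tissue parameters". The SAP also lists lesion count as a baseline characteristic, though that does not show that several lesions will be analysed for perfusion. Extra regions could raise the df above 1, but with correlated errors only partly: two regions correlated 0.5 give 2 / (1 + 0.5²) = 1.6 effective df. The 1-df statement is therefore limited to one parameter in one region.
- **Perfusion CT is a cross-check.** SAP 5.4 compares changes in the two modalities at the same timepoints. That gives some protection against a chance agreement in one of them, but CT reproducibility is estimated from a single pair in the same way.

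**Conclusion.** The point holds as a modest improvement. For one parameter in one region, the planned yardstick has 1 df and is too imprecise to separate change from noise in a single patient. A pooled SD from scans already scheduled is usually closer to a patient's true SD, under the error assumptions above and provided true SDs vary between patients with a CV below about 0.9.

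A reader might infer that the blood-flow endpoint as a whole is unsound. The documents do not support that. The planned summaries for all patients and by disease (Protocol 9.4, 9.4.5) do not use the own-pair SD, and the primary endpoints and sample size are unaffected. The 1-df arithmetic is certain given one pair; the advantage of pooling depends on how similar the patients' repeatability is, which the documents do not show.

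**What to change.** Add to SAP 5.4, for each DCE-MRI and perfusion-CT parameter:

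1. Estimate one within-patient SD with its 95% CI from all Visit 1–2 pairs, overall and by disease, on the log scale where spread grows with the level.
2. Define change as Visit 4 minus the mean of Visits 1 and 2, on the same scale.
3. On each individual plot, show the patient's own Visit 1–2 pair together with t(df) × √1.5 × the pooled SD as a reference limit.
4. State that the limit is descriptive and not a test, and give the number of values expected outside it by chance.

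The cost is SAP wording and a little programming, with no new scans. The price in assumptions should be written down: similar repeatability across patients, and Visit 1–2 variability that also applies at Visit 4. About 12 differences can check this only roughly. If one disease had twice the SD of the other (6 patients each), the limit pooled over 12 would mark 0.7% of unchanged values in one group and 12% in the other; pooling by disease restores 5% in each. It does not cure differences between individual patients, which is why the own pairs must stay on the plots. Each missing scan also lowers the df.
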